### 3. OBJECTIVES AND ENDPOINTS

Table 5 presents the objectives and endpoints.

**Table 5:** Objectives and Endpoints

Objectives	Endpoints
Primary	
To evaluate the efficacy of ruxolitinib cream in combination with NB-UVB in participants with vitiligo.	Change from baseline in T-VASI at Week 48.
Secondary	
To evaluate the safety and tolerability of ruxolitinib cream in combination with NB-UVB.	Occurrence of AEs and evaluation of vital signs and laboratory data.
To further evaluate the efficacy of ruxolitinib cream in combination with NB-UVB in participants with vitiligo.	
 
Proportion of participants achieving F-VASI50/75/90 at each postbaseline visit.
 
Proportion of participants achieving T-VASI50/75/90 at each postbaseline visit.
 
Change and percentage change from baseline in F-VASI/T-VASI at each postbaseline visit.
 
Change and percentage change from baseline in F-BSA/T-BSA at each postbaseline visit.
 

To evaluate the ruxolitinib PK in plasma after treatment with ruxolitinib cream in combination with NB-UVB.	Population-based (trough) plasma concentrations of ruxolitinib at Weeks 4, 12, and 16.

**Table 5:** Objectives and Endpoints (Continued)

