Application instructions:	A thin film is applied BID to depigmented vitiligo areas.
Packaging and labeling:	Ruxolitinib cream will be provided in 60 g tubes. Each tube will be labeled as required per country requirement.
Storage:	Ambient (15°C-30°C/59°F-86°F)
Status of treatment in participating countries:	Investigational

**Table 7:** Study Treatment Information (NB-UVB)

Study treatment name:	NB-UVB (311-312 nm)
Dosage formulation:	Cleared medical device
Dosage levels:	Starting dose = 200 mJ/cm  Increase dose by 10% at each visit until mild erythema lasting < 24 hours as reported by the participant. Hold dose at 1500 mJ/cm  – this may vary or be increased over the course of treatment. Dose information will be collected in the database.
Administration instructions:	Three times a week; not on consecutive days.
Status of treatment in participating countries:	Standard of care

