# 9.3. Recording and Follow-Up of Adverse Events and/or Serious Adverse Events

#### **Adverse Event and Serious Adverse Event Recording**

An AE/SAE that begins or worsens after informed consent is signed should be recorded on the
Adverse Event Form in the eCRF. AEs/SAEs should be reported for enrolled participants, but only
SAEs need to be reported for screen failure participants. For enrolled participants, conditions that
were present at the time informed consent was given should be recorded on the Medical History
Form in the eCRF. For detailed information, refer to the eCRF guidelines.

- When an AE/SAE occurs, it is the responsibility of the investigator to review all documentation (eg, hospital progress notes, laboratory reports, and diagnostic reports) related to the event.
- The investigator (or delegate) will then record all relevant AE/SAE information in the eCRF.
- It is **not** acceptable for the investigator to send photocopies of the participant's medical records in lieu of completing the Adverse Event Form in the eCRF.
- There may be rare instances when copies of medical records for certain cases are requested. In this case, all participant identifiers, with the exception of the participant number, will be redacted by the site staff on the copies of the medical records before submission. These records can be submitted to Incyte Pharmacovigilance by email/fax per the contact information listed in the Study Reference Manual or as per SAE completing guidelines.
- The investigator will attempt to establish a diagnosis of the event based on signs, symptoms, and/or other clinical information. Whenever possible, the diagnosis (not the individual signs/symptoms) will be documented as the AE/SAE. When a clear diagnosis cannot be identified, each sign or symptom should be reported as a separate AE/SAE.

To the extent possible, each AE/SAE should be evaluated to determine the following:

- The severity grade (CTCAE v5.0 Grade 1 to 5). See below for further instructions on the assessment of intensity.
- Whether there is at least a reasonable possibility that the AE is related to the study cream: suspected (yes) or not suspected (no). See below for further instructions on the assessment of causality.
- The start and end dates, unless unresolved at the final safety follow-up visit.
- The action taken with regard to study cream as a result of the AE/SAE(s).

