#### **Assessment of Causality**

- The investigator is obligated to assess the relationship between study cream and each occurrence of each AE/SAE.
- A "reasonable possibility" of a relationship conveys that there are medical facts, evidence, and/or arguments to suggest a causal relationship, rather than that a relationship cannot be ruled out.
- The investigator will use clinical judgment to determine the possibility of a relationship.
- The investigator will also consult the RSI in the IB or Product Information for ruxolitinib cream, or marketed products, respectively, in making their assessment.
- Alternative causes, such as underlying or concurrent disease(s), concomitant therapy, and other risk factors, as well as the temporal relationship of the event to study cream application, will be considered and investigated.
- For each AE/SAE, the investigator **must** document in the medical notes that they has reviewed the AE/SAE and has provided an assessment of causality.
- With regard to assessing causality of SAEs:
  - There may be situations in which an SAE has occurred and the investigator has minimal information to include in the initial report. However, the causality assessment is one of the criteria used when determining regulatory reporting requirements. Therefore, it is very important that the investigator always make an assessment of causality based on the available information for every event before the initial transmission of the SAE.
  - The investigator may change their opinion of causality in light of follow-up information and submit the updated causality assessment.

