## **Serious Adverse Event Reporting**

- Information about all SAEs is collected and recorded on the Adverse Event Form in the eCRF.
- The investigator must report within 24 hours of learning of its occurrence any SAE via the EDC system (primary method) or by completing the Serious Adverse Event Report Form in English (only if the EDC system is not available). The contact information for Incyte Pharmacovigilance by email/fax is listed in the Study Reference Manual or as per the Incyte Reference Guide for Completing the Serious Adverse Event Report Form.
- In circumstances where the EDC system is not accessible for reporting SAE information (initial and/or follow-up SAE information) to the sponsor within 24 hours, refer to the Incyte Reference Guide for Completing the Serious Adverse Report Form. Once the EDC system is functional, the SAE report should be retrospectively added to the EDC system and follow-up should be completed through the EDC. The original copy of the Serious Adverse Event Report Form and the email or facsimile confirmation sheet must be kept at the study site (refer to the Incyte Reference Guide for Completing the Serious Adverse Event Report Form or Study Reference Manual for details and for the email address or fax number).
- Follow-up information is also recorded in the eCRF and transmitted to Incyte Pharmacovigilance via the EDC system. The follow-up report should include information that was not provided previously, such as the outcome of the event, treatment provided, action taken with study cream because of the SAE (eg, application amount reduced, interrupted, or discontinued), or participant disposition (eg, continued or withdrew from study participation). Each recurrence, complication, or progression of the original event should be reported as follow-up to that event, regardless of when it occurs.

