## 10.4.2. Safety Analysis

Safety is being evaluated as a secondary objective in this study. Safety analyses will be conducted using the safety population and are summarized in Table 15.

**Table 15:** Safety Analyses

Endpoint	Statistical Analysis Methods		
Secondary	Adverse Events		
	A TEAE is any AE either reported for the first time or worsening of a pre-existing event after first application of study cream. Analysis of AEs will be limited to TEAEs, but data listings will include all AEs regardless of their timing to study cream application. Adverse events will be coded using MedDRA and tabulated by preferred term and system organ class. Severity of AEs will be based on the CTCAE v5.0 using Grades 1 through 5.		
	The subset of AEs considered by the investigator to have a relationship to study cream will be considered to be treatment-related AEs. If the investigator does not specify the relationship of the AE to study cream, then the AE will be considered treatment-related. The incidence of AEs and treatment-related AEs will be tabulated.		
	Clinical Laboratory Tests		
	Actual values and changes from baseline in clinical laboratory test results will be summarized using descriptive statistics. Laboratory test values outside the normal range will be assessed for severity based on the normal ranges for the clinical reference laboratory. The incidence of abnormal laboratory values will be tabulated.		
	Laboratory data will be classified into Grades 1 through 5 using CTCAE v5.0.		
	Shift tables from baseline to the worst postbaseline value using CTCAE grade will be tabulated.		
	Vital Signs		
	Descriptive statistics and mean change from baseline will be determined for vital signs (blood pressure, pulse, respiratory rate, and body temperature) at each assessment time.		

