9.2. Adverse Events

9.2.1. Adverse Event Definitions

A TEAE is any AE either reported for the first time or worsening of a pre-existing event after first application of study drug and within 30 days of the last application of study drug. For participants who have NB-UVB phototherapy added, the first application date is period-specific, and the end date is 30 days after the last application date in this period, or the day before the first application date in the next period, whichever comes first. Analysis of AEs (as discussed below) will be limited to TEAEs, but data listings will include all AEs regardless of their timing in relation to study drug application.

Adverse events will be tabulated by MedDRA PT and SOC. Severity of AEs will be graded using the NCI CTCAE v5. The CTCAE reporting guidelines and grading details are available on the Cancer Therapy Evaluation Program website.

The subset of AEs considered by the investigator to be related to study drug will be considered to be treatment-related AEs. If the investigator does not specify the relationship of the AE to study drug, the AE will be considered to be treatment-related. The incidence of AEs and treatment-related AEs will be tabulated. Serious AEs will also be tabulated.

Any missing onset date, causality, or severity must be queried for resolution. Unresolved missing causality and severity will be handled according to the following rules:

- An unresolved missing causality will be considered treatment-related.
- An unresolved missing severity will be identified as an unknown severity.

For purposes of analysis, all AEs will be considered TEAEs unless the AE can unequivocally be defined as not treatment-emergent.

Application site reactions are AEs that occur at the site of drug application. A summary of ASRs will be provided.

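### The safety objective covers cream plus NB-UVB, but relatedness is tied to the cream (protocol) or to an undefined study drug (SAP), and AE-driven NB-UVB stops have no named display

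*SAP*

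**What the plan says.** **Objective.** Protocol 3 sets the first secondary objective as "To evaluate the safety and tolerability of ruxolitinib cream in combination with NB-UVB", and SAP 2.2 repeats it. Protocol 6.1 lists NB-UVB in Table 7 as a study treatment alongside the cream.

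**Protocol, causality and action taken.** Under Assessment of Causality in 9.3: "The investigator is obligated to assess the relationship between study cream and each occurrence of each AE/SAE". The recording items in 9.3 ask whether the event may be related to the study cream and what was done with the study cream. The SAE reporting text in 9.4 also asks about action with the cream.

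**Protocol, analysis.** In Table 15 (section 10.4.2), the events counted are those "considered by the investigator to have a relationship to study cream will be considered to be treatment-related AEs".

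**SAP.** Section 9.2.1 gives the corresponding definition for study drug: "The subset of AEs considered by the investigator to be related to study drug will be considered to be treatment-related AEs". Section 9.2.2 uses the same term for AE-driven interruption and discontinuation. The SAP does not define it.

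**One exception.** The note to the Appendix A tables, which explains the Cohort A of Table 3.2.8.3, counts TEAEs related to either the cream or NB-UVB.

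**Stopping NB-UVB.** Protocol 4.1 lets a participant stop NB-UVB and carry on with the cream. Protocol 8.3.1 makes the investigator responsible for following up AEs that caused discontinuation of either agent.

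**The concern.** The objective is about a combination, while the relatedness definition in Table 15 concerns one component. A skin reaction that the investigator attributes to the light alone would be recorded as not related to the cream, and would then drop out of the treatment-related count that readers look to for the combination. The rule that missing causality counts as related does not help, because the cream causality would not be missing.

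The second gap concerns tolerability. NB-UVB is the component added at Week 12 and can be stopped alone. How often it was held or stopped for an AE is a basic tolerability result, and no named display would give it.

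**Working it through.** The documents state no figure to reproduce. The check is mainly textual, with a calculation for scale.

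**Step 1. What study drug means in the SAP.**

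| Place | Points to |
|---|---|
| SAP 6.5, headed as study drug compliance, counts cream applications; NB-UVB has its own section, 6.6 | Cream |
| SAP 1 ties the 30-day follow-up to the last cream application, alone or with NB-UVB; SAP 3 ties it to the last application of study drug | Can be read as the regimen |
| Note to Table 3.2.8.3 counts relatedness to either agent | A wider meaning, for one table |
| SAP 11.1 declares no change to protocol-defined analyses | If study drug includes NB-UVB, the SAP departs from Table 15 without saying so |

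The term is ambiguous. Whichever reading is intended, some text needs correcting.

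**Step 2. Follow one event.** Take a TEAE in Group A judged due to NB-UVB and not to the cream. Under Table 15, or the cream reading of the SAP:

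- It is absent from Tables 3.2.8.1 and 3.2.8.2, the treatment-related row of Table 3.2.1.1, and Listing 2.7.4.
- It is also absent from Table 3.2.9.1 if Grade 3 or higher, and from Table 3.2.10.1 if serious.
- It is present as related in Table 3.2.8.3 (by preferred term only), provided the CRF records NB-UVB causality. If it does not, that table cannot be filled as its note describes.
- It is present in the all-causality TEAE tables and listings. If it occurs where cream is applied, it may also be an application site reaction, which SAP 9.2.1 defines by location.

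**Step 3. Action-taken displays.** There are four: Tables 3.2.12.1 and 3.2.13.1, and Listings 2.7.2 and 2.7.6. SAP 9.2.2 adds two items to the overall summary (Table 3.2.1.1). None names NB-UVB. The title of Table 3.2.12.1 names no agent, but SAP 9.2.2 specifies study drug for it. The NB-UVB displays that are named, Table 3.1.3 and Listing 2.4.7, concern compliance.

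**Step 4. Scale.** Inputs: about 50 participants (SAP 3.3) and a 21.2% T-VASI25 rate at Week 12 in the earlier phase 2 study (Protocol 2.4).

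- Expected Group A = 50 × (1 − 0.212) = 39.4, about 39.
- The denominator of 21.2% is not stated. If it is 33, the rate is 7/33; the same arm's 12.1%, 30.3%, 36.4% and 45.5% fit 4, 10, 12 and 15 of 33. The exact 95% interval is then 9.0% to 38.9%, so Group A = 50 × (1 − 0.389) to 50 × (1 − 0.090) = 30.5 to 45.5, about 31 to 46.
- The chance of at least one AE-driven NB-UVB stop among 39 is 1 − (1 − q)^39. For assumed true rates q of 2%, 5% and 10% this is 55%, 87% and 98%. The documents give no such rate.
- Protocol 2.3 reports AEs in 4 of 19 participants on add-on NB-UVB, none related to treatment. The exact two-sided 95% upper limit for 0/19 is 1 − 0.025^(1/19) = 17.6%, and 0.176 × 39 = 6.9. That experience is compatible with none to about 7 of 39. It is not an estimate of affected events: the minimum exposure was 12 weeks against 36 planned here, and treatment is not defined there.

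**The case against.** Several points on the other side stand.

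- **The wording is loose.** A reader might infer that study cream cannot be shorthand for both treatments, because Protocol 8.3.1 and 8.3.5 name both agents where both are meant. The documents do not support that. Protocol 8.3.5 and 9.1 state nearly the same rule for laboratory abnormalities, one naming both agents and the other only the cream. Relatedness is also worded more widely in 7.1.2, 8.3.1 and 9.4, which mention treatment or procedures. Intent cannot be read from the wording; the point rests on what Table 15 and 9.3 literally ask for.
- **NB-UVB attribution is planned in one place.** It would be wrong to say that NB-UVB relatedness is reported nowhere. The SAP was written against a CRF already approved on 18 FEB 2022, and the Table 3.2.8.3 note suggests that NB-UVB causality may be collected.
- **Unseen material.** The CRF and table shells are not supplied, and Listing 2.7.7 is skipped in the public numbering. Appendix A may be modified without an SAP amendment where the nature of the analysis is unaffected.
- **NB-UVB is a cleared device and standard of care (Table 7).** Centring relatedness on the investigational cream is partly a sponsor's choice. But the stated objective is the combination, and Table 15 does not match it.

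A reader might also infer contradictions over the end-of-treatment visit when the cream stops, or over how long AEs are collected. These are not clear. Protocol 7.1.2 and 8.7 only call for a visit, the 30 days in 8.3.1 is a minimum, and SAP 9.2.1 treats an AE as treatment-emergent unless it is unequivocally not.

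**Conclusion.** The concern holds in two parts. The Table 15 definition is wrong as written for a combination objective, and the SAP's undefined term does not repair it. Adding displays of AE-driven NB-UVB stops is a cheap improvement.

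No event is lost. What is at risk is attribution to NB-UVB, outside one table, and the count of AE-driven NB-UVB interruptions and discontinuations. The first part applies under Table 15 as written or the cream reading of study drug. The second rests on the displays named in the SAP. Roughly 39 participants would be exposed to NB-UVB if the earlier response rate carries over; how many would have an affected event is unknown and could be none. Confidence is medium, because the CRF and shells could already hold the needed data.

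**What to change.** 1. **Definition.** In SAP 9.2.1, define treatment-related as related to the cream or to NB-UVB, in line with the Table 3.2.8.3 note. Define study drug, and show attribution to cream, to NB-UVB and to either. Align Protocol 9.3 and Table 15.
2. **Displays.** In SAP 9.2.2 and Appendix A, add rows to Table 3.2.1.1 and a table or listing of Group A TEAEs leading to NB-UVB interruption and to NB-UVB discontinuation. The SAP already allows a listing when 5 or fewer participants would appear.
3. **Data.** Confirm that the eCRF records causality and action taken for NB-UVB separately from the cream. If it does not, add the two fields and query the existing Group A AEs.

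**Cost.** If the fields exist, the work is definition wording, a few table rows and two displays that may be short listings. If not, add two eCRF fields and a round of queries. The downside is that a few more events will be labelled treatment-related.

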9.2.2. Adverse Event Summaries

An overall summary of AEs by treatment group will include the following:

- Number (%) of participants reporting any TEAEs
- Number (%) of participants reporting any serious TEAEs
- Number (%) of participants reporting any Grade 3 or higher TEAEs
- Number (%) of participants reporting any treatment-related TEAEs
- Number (%) of participants who temporarily interrupted study drug because of TEAEs
- Number (%) of participants who permanently discontinued study drug because of TEAEs
- Number (%) of participants who had a fatal TEAE

The following summaries will be produced by MedDRA term (if 5 or fewer participants appear in a table, a listing may be appropriate):

- Summary of TEAEs by SOC, PT, and maximum severity
- Summary of TEAEs by SOC and PT
- Summary of TEAEs by PT in decreasing order of frequency
- Summary of Grade 3 or higher AEs by SOC and PT
- Summary of Grade 3 or higher AEs by PT in decreasing order of frequency
- Summary of serious TEAEs by SOC and PT
- Summary of serious TEAEs by PT in decreasing order of frequency
- Summary of ASRs by SOC and PT
- Summary of ASRs by PT in decreasing order of frequency
- Summary of treatment-related TEAEs by SOC and PT
- Summary of treatment-related TEAEs by PT in decreasing order of frequency
- Summary of Grade 3 or higher treatment-related TEAEs by SOC and PT

CONFIDENTIAL

- Summary of treatment-related serious TEAEs by SOC and PT
- Summary of TEAEs with a fatal outcome by SOC and PT
- Summary of TEAEs leading to dose interruption of study drug by SOC and PT
- Summary of TEAEs leading to discontinuation of study drug by SOC and PT

9.3. Clinical Laboratory Tests

9.3.1. Laboratory Value Definitions

All laboratory assessments will be performed using a central laboratory, except for urine pregnancy tests (when applicable). Laboratory values and change from baseline values will be summarized descriptively by visit; non-numeric test values will be tabulated when necessary.

The baseline value will be determined using the last nonmissing value collected before the first application, prioritizing scheduled assessments for baseline identification over unscheduled visits. The last record before application in the highest priority will be considered the baseline record. For baseline laboratory candidates with the same date and time in the same priority category, additional rules may be provided after consultation with the medical monitor to delineate which value will be defined as baseline.

9.3.2. Laboratory Value Summaries

Actual values and changes from baseline in clinical laboratory test results will be summarized using descriptive statistics. Laboratory test values outside the normal range will be assessed for severity based on the normal ranges for the clinical reference laboratory. The incidence of abnormal laboratory values will be tabulated.

Laboratory data will be classified into Grades 1 through 5 using CTCAE v5.0. The following summaries will be produced for the laboratory data:

- Number and percentage of participants with worst postbaseline CTCAE grade (regardless of baseline value). (Note: Each participant will be counted only for their worst grade observed postbaseline.)
- Shift tables from baseline to the worst postbaseline value using CTCAE grade.

In addition, box plots will be provided for hemoglobin, platelet counts, neutrophils, leukocytes, lymphocytes, erythrocytes, and reticulocytes.

9.4. Vital Signs

Descriptive statistics and mean change from baseline will be determined for vital signs (blood pressure, pulse, respiratory rate, and body temperature) at each assessment time.

Criteria for clinically notable vital sign abnormalities are defined in Table 4. The abnormal values for participants exhibiting clinically notable vital sign abnormalities will be listed along with their assigned treatment group. Alert vital signs are defined as an absolute value outside the defined range and percentage change > 25%. The abnormal values for participants exhibiting alert vital sign abnormalities will be listed.

Parameter	High Threshold	Low Threshold
Systolic blood pressure	> 155 mmHg	< 85 mmHg
Diastolic blood pressure	> 100 mmHg	< 40 mmHg
Pulse	> 100 bpm	< 45 bpm
Temperature	> 38°C	< 35.5°C
Respiratory rate	> 20 breaths/min	< 8 breaths/min

Table 4: Criteria for Clinically Notable Vital Sign Abnormalities for ≥ 18 Years Old

